4.2 Trial Treatments

The treatment plan is outlined in Table 2

Table 2: Treatment Schedule. Treatment with nivolumab and axitinib begins on C1D1.

Drug	Dose/Potency	Dose Frequency	Route of Administration	Regimen/Treatment Period
Nivolumab	480 mg	Q4W	IV infusion	Day 1 of each 4-week cycle

Drug	Dose/Potency	Dose Frequency	Route of Administration	Regimen/Treatment Period
Axitinib	5 mg	Twice daily	Oral	Daily

4.2.2 Patient Compliance

Patients will be required to return all bottles of axitinib at the beginning of each 4-week period. The number of tablets remaining will be documented and recorded.

4.2.3 **Duration of Therapy**

Treatment will continue for up to 2 years or until progression of disease or unacceptable toxicities.

4.2.4 Starting Dose and Modifications

4.2.4.1 Nivolumah

The Nivolumab dose if 480 mg IV every 4 weeks.

Adverse events (both non-serious and serious) associated with nivolumab exposure may represent an immunologic etiology. These adverse events may occur shortly after the first dose or several months after the last dose of treatment. Nivolumab must be withheld for drug-related toxicities and severe or life-threatening AEs as per table 3 below. See Section 4.3.1 for supportive care guidelines, including use of corticosteroids.

At the end of the study period, Bristol-Myers Squibb Company will not continue to supply study drug to subjects/investigators unless the Sponsor-Investigator chooses to extend the study. The treating physician is responsible to ensure that the subject receives appropriate standard of care or other appropriate treatment.

No modifications in the dose of nivolumab are permitted. Dose delays are permitted, as outlined below.

Table 3: Nivolumab Dose Delay and Discontinuation Guidelines for Drug-Related Adverse Events

Toxicity	Hold Treatment for Grade	Timing for Restarting Treatment	Treatment Discontinuation
Diarrhea/Colitis	2-3	Toxicity resolves to Grade 0-1	Toxicity does not resolve within 12 weeks of last dose or inability to reduce corticosteroid to 10 mg or less of prednisone or equivalent per day within 12 weeks

Toxicity	Hold Treatment for Grade	Timing for Restarting Treatment	Treatment Discontinuation
	4	Permanently discontinue	Permanently discontinue
AST, ALT, or Increased	2	Toxicity resolves to Grade 0-1	Toxicity does not resolve within 12 weeks of last dose
Bilirubin	3-4	Permanently discontinue (see exception below) ^a	Permanently discontinue
Type 1 diabetes mellitus (if new onset) or Hyperglycemia	T1DM or 3-4	Hold for new onset Type 1 diabetes mellitus or Grade 3-4 hyperglycemia associated with evidence of beta cell failure	Resume when patients are clinically and metabolically stable
Hypophysitis	2-4	Toxicity resolves to Grade 0-1. Therapy with can be continued while endocrine replacement therapy is instituted	Toxicity does not resolve within 12 weeks of last dose or inability to reduce corticosteroid to 10 mg or less of prednisone or equivalent per day within 12 weeks
Hyperthyroidism	3	Toxicity resolves to Grade 0-1	Toxicity does not resolve within 12 weeks of last dose or inability to reduce corticosteroid to 10 mg or less of prednisone or equivalent per day within 12 weeks
	4	Permanently discontinue	Permanently discontinue
Hypothyroidism		Therapy with can be continued while thyroid replacement therapy is instituted	Therapy with can be continued while thyroid replacement therapy is instituted
Infusion Reaction	2 ^b	Toxicity resolves to Grade 0-1	Permanently discontinue if toxicity develops despite adequate premedication
	3-4	Permanently discontinue	Permanently discontinue
Pneumonitis	2	Toxicity resolves to Grade 0-1	Toxicity does not resolve within 12 weeks of last dose or inability to reduce corticosteroid to 10 mg or less of prednisone or equivalent per day within 12 weeks
	3-4	Permanently discontinue	Permanently discontinue
Renal Failure or Nephritis	2	Toxicity resolves to Grade 0-1	Toxicity does not resolve within 12 weeks of last dose or inability to reduce corticosteroid to 10 mg or less of prednisone or equivalent per day within 12 weeks
	3-4	Permanently discontinue	Permanently discontinue
All Other Drug-Related Toxicity ^c	3 or Severe	Toxicity resolves to Grade 0-1	Toxicity does not resolve within 12 weeks of last dose or inability to reduce corticosteroid to 10 mg or less of prednisone or equivalent per day within 12 weeks
	4	Permanently discontinue	Permanently discontinue

Note: Permanently discontinue for any severe or Grade 3 drug-related AE that recurs or any life-threatening event.

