4.1.2 Subject Exclusion Criteria

The subject will be excluded from the trial if the subject:

- 1. Prior history of Grade 3 or 4 immune-related adverse events or immune-related adverse events requiring discontinuation of prior therapies.
- 2. History of hypertensive crisis or hypertensive encephalopathy
- 3. Significant thrombotic (e.g, deep vein thrombosis or pulmonary embolism) or hemorrhagic event within 6 months prior to enrollment).
- 4. Has a history of prior immune-related adverse event due to an anti-PD1 or anti-CTLA4 that has not resolved to grade 1 on a steroid dose of prednisone 10 mg or less at the time of study entry (excluding vitiligo and endocrine toxicity).
 - Patients with prior myocarditis or other immune-mediated cardiac adverse events are excluded regardless of grade.
 - Patients with prior Guillain-Barre syndrome, encephalitis, meningitis, or transverse myelitis are excluded regardless of grade.

- Patients with prior Stevens-Johnson syndrome or toxic epidermal necrolysis are excluded regardless of grade.
- 5. Has poorly controlled hypertension defined as systolic blood pressure (SBP) > 160 and/or diastolic blood pressure (DBP) > 100 despite antihypertensives. If subject is above this goal, treatment with anti-hypertensives to achieve better blood pressure control is permitted. Ambulatory blood pressure assessment is permitted if there is concern for discrepant blood pressure readings while patients are in clinic. Note: measurement of screening blood pressure (BP) reading is based on an average of 3 readings at least 2 minutes apart if the subject has an initial BP ≥150/90. Subjects with initial screening BP ≥150/90 mmHg can be treated with anti-hypertensive medication to achieve a well-controlled status and are eligible with reassessed SBP/DBP of < 160/100 mm Hg.
- 6. Has Class III or IV heart failure based on the New York Heart Association
- 7. Has had major surgery within 4 weeks of randomization. This does not include outpatient surgeries that do not require post-operative admission.
- 8. Has a diagnosis of immunodeficiency or is receiving systemic steroid therapy (greater than the equivalent of prednisone 10 mg daily, unless for prior endocrine toxicity) or any other form of immunosuppressive therapy within 7 days prior to the first dose of trial treatment. Premedication with steroids for contrast imaging studies is permitted.
- 9. Has a known history of active TB (Bacillus Tuberculosis).

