4.2.5 Timing of Dose Administration

Nivolumab: Trial treatment should be administered on Day 1 of each cycle after all procedures/assessments have been completed as detailed on the Trial Flow Chart (Section 6.0). Trial treatment may be administered up to 3 days before or after the scheduled Day 1 of each cycle due to administrative reasons.

All trial treatments will be administered on an outpatient basis.

Nivolumab 480 mg will be administered as a 30 minute IV infusion every 4 weeks. Sites should make every effort to target infusion timing to be as close to 30 minutes as possible. However, given the variability of infusion pumps from site to site, a window of -5 minutes and +10 minutes is permitted (i.e., infusion time is 30 minutes: -5 min/+10 min).

Nivolumab will be prepared and infused per institutional standards

Axitinib: Axitinib 5 mg PO twice daily, 12 hours apart, will be taken for the entire duration of treatment. Patients will be given specific instructions on how to take axitinib. If a dose is missed, it may be taken up to 8 hours later that same day.

Dosing interruptions of nivolumab and axitinib are permitted in the case of medical / surgical events or logistical reasons not related to study therapy (e.g., elective surgery, unrelated medical events, patient vacation, and/or holidays). Subjects should be placed back on study therapy within 3 weeks of the scheduled interruption, unless otherwise discussed with the Sponsor. The reason for interruption should be documented in the patient's study record.

Should the combination of nivolumab and axitinib be further investigated for the treatment of anti-PD1 refractory melanoma, given the potential for late onset immune-related toxicities for nivolumab, any such late toxicity will be considered in the determination of the final dose and dose schedule. The number of required dose reductions of axitinib will also be taken into full consideration.

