4.3 Rescue Medications & Supportive Care

4.3.1 Supportive Care Guidelines

Subjects should receive appropriate supportive care measures as deemed necessary by the treating investigator. Suggested supportive care measures for the management of adverse events with potential immunologic etiology are outlined below. Where appropriate, these guidelines include the use of oral or intravenous treatment with corticosteroids as well as additional anti-inflammatory agents if symptoms do not improve with administration of corticosteroids. Note that several courses of steroid tapering may be necessary as symptoms may worsen when the steroid dose is decreased. For each disorder, attempts should be made to rule out other causes such as metastatic disease or bacterial or viral infection, which might require additional supportive care. The treatment guidelines are intended to be applied when the investigator determines the events to be related to study drug(s).

Note: if after the evaluation the event is determined not to be related, the investigator does not need to follow the treatment guidance (as outlined below). Refer to Section 4.2.4 for dose modification.

It may be necessary to perform conditional procedures such as bronchoscopy, endoscopy, or skin photography as part of evaluation of the event.

For toxicities where the attribution is Nivolumab (immune mediated toxicity)

• Pneumonitis:

- For Grade 2 events, treat with systemic corticosteroids. When symptoms improve to Grade 1 or less, steroid taper should be started and continued over no less than 4 weeks.
- For Grade 3-4 events, immediately treat with intravenous steroids.
 Administer additional anti-inflammatory measures, as needed.
- o Add prophylactic antibiotics for opportunistic infections in the case of prolonged steroid administration.

• Diarrhea/Colitis:

Subjects should be carefully monitored for signs and symptoms of enterocolitis (such as diarrhea, abdominal pain, blood or mucus in stool, with or without fever) and of bowel perforation (such as peritoneal signs and ileus).

- All subjects who experience diarrhea/colitis should be advised to drink liberal quantities of clear fluids. If sufficient oral fluid intake is not feasible, fluid and electrolytes should be substituted via IV infusion. For Grade 2 or higher diarrhea, consider GI consultation and endoscopy to confirm or rule out colitis.
- o For **Grade 2 diarrhea/colitis**, administer oral corticosteroids.

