- For Grade 3 or 4 diarrhea/colitis, treat with intravenous steroids followed by high dose oral steroids.
- O When symptoms improve to Grade 1 or less, steroid taper should be started and continued over no less than 4 weeks.
- Type 1 diabetes mellitus (if new onset, including diabetic ketoacidosis [DKA]) or ≥ Grade 3 Hyperglycemia, if associated with ketosis (ketonuria) or metabolic acidosis (DKA)
 - o For **T1DM** or **Grade 3-4** Hyperglycemia
 - Insulin replacement therapy is recommended for Type I diabetes mellitus and for Grade 3-4 hyperglycemia associated with metabolic acidosis or ketonuria.

• Evaluate patients with serum glucose and a metabolic panel, urine ketones, glycosylated hemoglobin, and C-peptide.

• Hypophysitis:

- For Grade 2 events, treat with corticosteroids. When symptoms improve to Grade 1 or less, steroid taper should be started and continued over no less than 4 weeks. Replacement of appropriate hormones may be required as the steroid dose is tapered.
- o For **Grade 3-4** events, treat with an initial dose of IV corticosteroids followed by oral corticosteroids. When symptoms improve to Grade 1 or less, steroid taper should be started and continued over no less than 4 weeks. Replacement of appropriate hormones may be required as the steroid dose is tapered.

• Hyperthyroidism or Hypothyroidism:

Thyroid disorders can occur at any time during treatment. Monitor patients for changes in thyroid function (at the start of treatment, periodically during treatment, and as indicated based on clinical evaluation) and for clinical signs and symptoms of thyroid disorders.

- o **Grade 2** hyperthyroidism events (and **Grade 2-4** hypothyroidism):
 - In hyperthyroidism, non-selective beta-blockers (e.g. propranolol) are suggested as initial therapy.
 - In hypothyroidism, thyroid hormone replacement therapy, with levothyroxine or liothyroinine, is indicated per standard of care.

Grade 3-4 hyperthyroidism

Treat with an initial dose of IV corticosteroid followed by oral corticosteroids. When symptoms improve to Grade 1 or less, steroid taper should be started and continued over no less than 4 weeks. Replacement of appropriate hormones may be required as the steroid dose is tapered.

• Hepatic:

- For **Grade 2** events, monitor liver function tests more frequently until returned to baseline values (consider weekly).
 - Treat with IV or oral corticosteroids
- o For **Grade 3-4** events, treat with intravenous corticosteroids for 24 to 48 hours.

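### Table 3 sets no steroid-dose condition for restarting nivolumab, and its Grade 2 liver row lacks the 12-week steroid stop

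*Combined protocol and SAP*

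**What the plan says.** In Section 4.2.4.1, Table 3 has separate columns for when to hold nivolumab, when to restart it and when to stop permanently. For most held events the restart column rests on grade alone: "Toxicity resolves to Grade 0-1". Six rows add a steroid limb to the permanent-stop column: "inability to reduce corticosteroid to 10 mg or less of prednisone or equivalent per day within 12 weeks". These are colitis, hypophysitis, hyperthyroidism, pneumonitis, renal events and the row headed "All Other Drug-Related Toxicity". In the Grade 2 AST/ALT/bilirubin row the only stop is failure of the toxicity to resolve within 12 weeks.

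Section 4.3.1 sets out steroid treatment. For pneumonitis, colitis, hypophysitis, hyperthyroidism and renal events it says: "When symptoms improve to Grade 1 or less, steroid taper should be started and continued over no less than 4 weeks". The liver guidance is the same in substance, and Grade 2 liver events are to receive intravenous or oral corticosteroids. The section also warns: "Note that several courses of steroid tapering may be necessary as symptoms may worsen when the steroid dose is decreased".

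At entry, Section 4.1.2 is stricter. Exclusion 8 covers a patient who "is receiving systemic steroid therapy (greater than the equivalent of prednisone 10 mg daily, unless for prior endocrine toxicity") in the 7 days before first dosing. Exclusion 4 covers a prior immune-related event "that has not resolved to grade 1 on a steroid dose of prednisone 10 mg or less at the time of study entry", with vitiligo and endocrine toxicity excepted.

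**The concern.** The grade that permits restart is the grade at which the taper begins. A patient can therefore meet the restart condition on the first day of a taper that must last at least 4 weeks, while still on a treatment dose of steroid. Because symptoms can return as the dose falls, Grade 1 on a treatment dose is weaker evidence of recovery than Grade 1 on 10 mg or less. Nivolumab cannot be dose-reduced, so the re-dose is the full 480 mg.

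The liver row has a second gap. A Grade 2 event that has improved to Grade 1 but still needs high-dose steroid after 12 weeks meets the restart condition and triggers no stop in its own row. In the colitis or renal row, the same course would end treatment. The protocol gives no reason for the difference.

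**Working it through.** The plan states no figure on this point, so the check is a comparison of the rules.

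**Step 1. Rows that restart on Grade 0-1** (Table 3, Section 4.3.1 and Table 6)

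| Row, grade held | Steroid dose in restart cell | 12-week steroid stop | Steroid treatment prescribed |
|---|---|---|---|
| Diarrhea/colitis, 2-3 | No | Yes | Yes, with taper |
| AST/ALT/bilirubin, 2 | No | **No** | Yes, with taper |
| Hypophysitis, 2-4 | No | Yes | Yes, with taper |
| Hyperthyroidism, 3 | No | Yes | Yes, with taper |
| Infusion reaction, 2 | No | No | None listed |
| Pneumonitis, 2 | No | Yes | Yes, with taper |
| Renal, 2 | No | Yes | Yes, with taper |
| All other, 3 or severe | No | Yes | None specified |

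None of the 8 restart cells carries a steroid condition, and 6 of the 8 rows carry the 12-week stop. Of the two without it, the infusion-reaction row has no steroid treatment listed at Grade 2. Among the six rows with prescribed steroid treatment, 5 have the stop and the liver row does not. Footnote c, on physician-discretion holds for persistent Grade 2 other events, also has no steroid clause.

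**Step 2. Is there a limit elsewhere?** Section 4.2.4.1 refers to Section 4.3.1 for steroid use, and Section 4.3.1 refers back to Section 4.2.4 for dose modification. Neither limits the steroid dose at re-dosing. Section 4.2.5 deals only with scheduling: "Trial treatment may be administered up to 3 days before or after the scheduled Day 1 of each cycle due to administrative reasons". Exclusions 4 and 8 apply at entry.

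**Step 3. How far the entry criteria carry over.** Exclusion 8 applies whatever the reason for the steroid, apart from prior endocrine toxicity. Exclusion 4 is a direct match only for Grade 2 colitis, liver and renal events: exclusion 1 already bars prior Grade 3-4 immune events, exclusion 18 bars steroid-treated pneumonitis, and exclusion 4 itself excepts endocrine toxicity.

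**Step 4. How much a 10 mg condition could delay restart.** The protocol gives the minimum taper (4 weeks, 28 days) but not the starting dose or shape. Assume a linear taper to zero over 28 days from D0 mg/day. Days above 10 mg = 28 × (1 − 10/D0):

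- D0 = 20: 28 × 0.50 = 14.0 days
- D0 = 40: 28 × 0.75 = 21.0 days
- D0 = 60: 28 × 0.833 = 23.3 days
- D0 = 100: 28 × 0.90 = 25.2 days

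All are below the 28-day dosing interval, so under this assumption the condition moves a restart by at most one scheduled dose. At the earliest permitted restart, 28 × 10/D0 = 14.0, 7.0, 4.7 or 2.8 days of taper would remain. Longer tapers lengthen the delay.

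**The case against.** The strongest reply is that the permanent-stop column shows the intent. Its first limb, unresolved toxicity at 12 weeks, mirrors the restart condition, so its second limb, failure to get down to 10 mg, can be read as the other thing a held patient is waiting for. Table 8 also describes Grade 1 as needing no intervention, which sits badly with an event still on treatment-dose steroid. These readings are reasonable, but they do not close the gap. The stop cell joins the two limbs with an or, and the restart cell repeats only the first. Section 4.3.1 itself applies the Grade 1 label to patients whose taper has not yet begun. For the liver row there is no second limb from which to infer anything.

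Existing safeguards also count. Grade 3-4 pneumonitis, liver and renal events and Grade 4 colitis end treatment, as do recurrent Grade 3 events and any life-threatening event. Grade 2 liver events get more frequent testing, and non-resolution by 12 weeks stops treatment. Section 4.5 allows investigator withdrawal, Section 6.2 has toxicity monitoring and accrual halts, and Section 8.1 has monthly review. These limit the consequence and keep the point modest.

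The objection succeeds on the endocrine rows. Exclusions 4 and 8 both except endocrine toxicity, and the hypophysitis row lets therapy continue while hormone replacement is started. A steroid condition there would be stricter than the protocol's own first-dose standard.

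**Conclusion.** Both gaps are present in the text: no steroid-dose condition on restart, and no 12-week steroid stop for Grade 2 AST/ALT/bilirubin. Followed literally, Table 3 does not prevent a 480 mg re-dose above 10 mg/day prednisone. The liver omission is the clearer of the two.

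A reader might infer more, in three ways that the documents do not support.

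- That the protocol authorises re-dosing on high-dose steroid. It is silent, and an investigator may well taper first.
- That a chance of overlap between a dosing day and the taper can be quoted as the risk. Any such percentage depends on an assumed starting dose, taper shape and start day, and applies only after an event, steroid treatment, recovery and a decision to re-dose mid-taper.
- That Grade 4 hypophysitis can be restarted because the row covers Grades 2-4. The note under Table 3 stops treatment for any life-threatening event.

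Neither the number of patients affected nor the harm can be derived from the documents. The amendment is a modest safety improvement worth making because it is cheap. It does not touch the endpoint, the sample size of 31 or the error rates.

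**What to change.** 1. In the Grade 2 AST/ALT/bilirubin row, add the 12-week steroid stop in the words used by the other rows ("inability to reduce corticosteroid to 10 mg or less of prednisone or equivalent per day within 12 weeks").
2. In the restart cells for colitis Grade 2-3, AST/ALT/bilirubin Grade 2, pneumonitis Grade 2, renal Grade 2 and all other Grade 3, add: *and corticosteroid dose down to the equivalent of prednisone 10 mg/day or lower*. Add the same condition to footnote c for holds in which steroids were given.
3. Leave the hypophysitis and hyperthyroidism restart cells unchanged.

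This changes five restart cells, one stop cell and one footnote. It needs no new data, since Section 5.1.1.4 already records medications. The downside is that some restarts come later, by at most one four-weekly dose under the assumed minimum linear taper and by more with longer tapers. A few more patients may stop permanently after Grade 2 liver events. The change shortens the overlap between steroid taper and re-dosing but does not remove it.

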	1.5 ULN			
ACT (CCOT) = 1 ALT (CCDT)	≤ 2.5 X ULN OR			
AST (SGOT) and ALT (SGPT)	≤ 5 X ULN for subjects with liver metastases			
Coagulation				
International Normalized Datic (IND) or	≤1.5 X ULN unless subject is receiving anticoagulant therapy			
International Normalized Ratio (INR) or	as long as PT or PTT is within therapeutic range of intended use			
Prothrombin Time (PT)	of anticoagulants			
Astivated Partial Thrombonlastin Time	≤1.5 X ULN unless subject is receiving anticoagulant therapy			
Activated Partial Thromboplastin Time	as long as PT or PTT is within therapeutic range of intended use			
(aPTT)	of anticoagulants			
*Creatinine clearance should be calculated per institutional standard.				

- 9. Patients with brain metastases are permitted if they are asymptomatic or previously treated with CNS directed therapy with stable CNS disease for at least 2 weeks. Stable is defined as asymptomatic or not progressing on imaging.
- 10. Female patients of childbearing potential must have a negative urine or serum pregnancy test within 7 days from the time of registration. Also, within 24 hours prior to receiving the first dose of study medication then every 4 weeks while on treatment.
- 11. Female subjects of childbearing potential should be willing to use 2 methods of birth control or be surgically sterile or abstain from heterosexual activity for the course of the study and for 5 months after the last dose of study medication. Subjects of childbearing potential are those who have not been surgically sterilized or have not been free from menses for > 1 year.
- 12. Male subjects should agree to use an adequate method of contraception starting with the first dose of study therapy through 7 months after the last dose of study therapy.

Note: Abstinence is acceptable if this is the usual lifestyle and preferred contraception for the subject.

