4.2.4.2 Axitinib

Axitinib will be administered at the standard dosing of 5mg po twice daily.

^a For patients with liver metastasis who begin treatment with Grade 2 AST or ALT, if AST or ALT increases by greater than or equal to 50% relative to baseline and lasts for at least 1 week then patients should be discontinued.

b If symptoms resolve within one hour of stopping drug infusion, the infusion may be restarted at 50% of the original infusion rate (e.g., from 100 mL/hr to 50 mL/hr). Otherwise dosing will be held until symptoms resolve and the subject should be premedicated for the next scheduled dose; Refer to Table 5– Infusion Treatment Guidelines for further management details.

c Patients with intolerable or persistent Grade 2 drug-related AE may hold study medication at physician discretion. Permanently discontinue study drug for persistent Grade 2 adverse reactions for which treatment with study drug has been held, that do not recover to Grade 0-1 within 12 weeks of the last dose.

Table 4. Axitinib Dose Modification Guidelines for Drug-Related Adverse Events

Toxicity	Action	
Grade 4 non-hematologic toxicity considered related to axitinib per investigator judgment (including persistent nausea, vomiting, diarrhea, hypertension despite optimal medical therapy), excluding clinically manageable laboratory abnormalities (e.g. electrolytes).	Discontinue axitinib.	
Grade 3 non-hematologic toxicity considered related to axitinib per investigator judgment (including persistent nausea, vomiting, diarrhea, hypertension, proteinuria despite optimal medical therapy), excluding clinically manageable laboratory abnormalities (e.g. electrolytes).	Hold axitinib until recovery to Grade 0-1 or baseline and resume at the same dose level. If grade 3 toxicity reoccurs despite reduction, patient may be dose reduced by 1 dose level upon recovery to Grade 0-1 or baseline. Prompt palliative and supportive measures mandated per local standard of care (eg, antiemetic).	
Grade 3 Thrombocytopenia, ie, PLTS <50,000 mm3 (50.0 x 109/L) with bleeding.	Discontinue Axitinib	
Grade 3 hematologic toxicity considered related to axitinib per investigator judgment	 -Hold axitinib until recovery to Grade ≤ 2 or baseline and resume axitinib at the same dose level. -If grade 3 toxicity reoccurs, patient may either be held until recovery and continued at same dose, or undergo dose reduction by 1 dose level. 	

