5.2.3 Evaluating Adverse Events

An investigator who is a qualified physician will evaluate all adverse events according to the NCI Common Terminology for Adverse Events (CTCAE), version 5.0. Any adverse event which changes CTCAE grade over the course of a given episode will have each change of grade recorded on the adverse event case report forms/worksheets.

All adverse events regardless of CTCAE grade must also be evaluated for seriousness.

Table 8: Evaluating Adverse Events

An investigator who is a qualified physician, will evaluate all adverse events as to:

V4.0 CTCAE Grading	Grade 1	Mild; asymptomatic or mid symptoms; clinical or diagnostic observations only; intervention not indicated.	
	Grade 2	Moderate; minimal, local or noninvasive intervention indicated; limiting age-appropriate instrumental ADL.	
	Grade 3	Severe or medically significant but not immediately life-threatening; hospitalization or prolongation or hospitalization indicated; disabling; limiting self-care ADL.	
	Grade 4	Life threatening consequences; urgent intervention indicated.	
	Grade 5	Death related to AE	
Seriousness	A serious adverse event is any adverse event occurring at any dose or during the course of study treat that:		
	†Results in dea	ath; or	
	†Is life threatening; or places the subject, in the view of the investigator, at immediate risk of death from the event as it occurred (Note: This does not include an adverse event that, had it occurred in a more severe form, might have caused death.); or		
		persistent or significant disability/incapacity (substantial disruption of one's ability to life functions); or	
	†Results in or prolongs an existing inpatient hospitalization (hospitalization is defined as an inpatient admission, regardless of length of stay, even if the hospitalization is a precautionary measure for continued observation. (Note: Hospitalization for an elective procedure to treat a pre-existing condition that has not worsened is not a serious adverse event. A pre-existing condition is a clinical condition that is diagnosed prior to the use of study treatment and is documented in the patient's medical history.); or		
	†Is a congenit diagnosis);or	al anomaly/birth defect (in offspring of subject taking the product regardless of time to	
	Is a new cancer	r (that is not a condition of the study) (although not serious per ICH definition, is reportable);	

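### Table 3 and its closing note give opposite nivolumab instructions for Grade 4 hyperglycemia and Grade 4 hypophysitis, and nothing says which governs

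*Combined protocol and SAP*

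**What the plan says.** Section 4.2.4.1 makes Table 3 the operative instruction for withholding nivolumab. By its title the table covers drug-related adverse events.

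- **Closing note to Table 3:** "Permanently discontinue for any severe or Grade 3 drug-related AE that recurs or any life-threatening event". It lists no exceptions.
- **Grade 4 in Table 8 (Section 5.2.3):** "Life threatening consequences; urgent intervention indicated".
- **Type 1 diabetes/hyperglycemia row** (new-onset diabetes or Grade 3-4): "Hold for new onset Type 1 diabetes mellitus or Grade 3-4 hyperglycemia associated with evidence of beta cell failure". Its discontinuation column holds no stopping criterion, only "Resume when patients are clinically and metabolically stable".
- **Hypophysitis row** (hold at Grades 2-4), restart cell: "Toxicity resolves to Grade 0-1. Therapy with can be continued while endocrine replacement therapy is instituted". Its discontinuation column stops nivolumab only for failure to resolve, or failure to taper steroids, within 12 weeks.
- **Hypothyroidism row:** no hold grade. Treatment may go on while replacement is started.
- **Hyperthyroidism row at Grade 4:** "Permanently discontinue", in both columns.
- **AST/ALT/bilirubin rows:** Grade 2 is held until Grade 0-1 and discontinued if unresolved within 12 weeks of the last dose. Grade 3-4 is a permanent stop, with a pointer to footnote a.
- **Footnote a** concerns patients with liver metastasis whose transaminases are already Grade 2 at the start, and gives this stopping trigger: "if AST or ALT increases by greater than or equal to 50% relative to baseline and lasts for at least 1 week then patients should" come off treatment. Table 1 (Section 4.1.1) admits AST and ALT at "≤ 5 X ULN for subjects with liver metastases".

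**The concern.** A row that resumes a drug after a Grade 4 event and a note that ends it after a life-threatening event cannot both be followed when the event is both. The reader is told neither that the row is an exception to the note nor that the note overrides the row.

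What is at stake is first a patient-safety decision: whether nivolumab is given again after such an event. The second consequence is for reporting. Safety is a secondary objective (Section 2.4), and Section 6.4.3 tabulates withdrawals from study medication. If sites resolve the conflict differently, those counts partly reflect which line of the table was read.

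**Working it through.** The plan states no figure to reproduce. The check sets each Table 3 category at Grade 4 beside the closing note, using Table 8's description of Grade 4.

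| Table 3 category | Row instruction at Grade 4 | Against the note |
|---|---|---|
| Diarrhea/colitis | Permanent stop | Agrees |
| AST/ALT/bilirubin | Permanent stop, subject to footnote a | Agrees, apart from the footnote |
| Type 1 diabetes/hyperglycemia | Hold, then resume when stable | Opposite |
| Hypophysitis | Hold, then restart at Grade 0-1 | Opposite |
| Hyperthyroidism | Permanent stop | Agrees |
| Hypothyroidism | Continue with replacement | Opposite at Grade 4 only |
| Infusion reaction | Permanent stop | Agrees |
| Pneumonitis | Permanent stop | Agrees |
| Renal failure/nephritis | Permanent stop | Agrees |
| All other drug-related | Permanent stop | Agrees |

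The count is 7 + 3 = 10. Two rows return the patient to nivolumab after a hold, one never holds it, and seven match the note, one of these subject to footnote a.

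**Is precedence settled elsewhere?** Section 4.3.1 foresees Grade 4 for all three conflicting conditions, but covers steroids, insulin and hormone replacement, not re-dosing; for dose changes it points back to Section 4.2.4. Section 4.5 refers to Section 5.2.1.2 for unacceptable adverse experiences. No section of that number appears in the supplied text; Section 5.2.1 concerns pregnancy reporting.

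**Hypophysitis cell.** One sentence makes recovery to Grade 0-1 the condition for restarting. The next says therapy can be continued during replacement. The cell does not say whether the second replaces the hold or describes what happens after recovery. The missing drug name may come from text extraction and is not counted.

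**Liver rows.** Footnote a is cited only on the Grade 3-4 row, and its only instruction is a stopping trigger relative to baseline. For an entry value of b × ULN the trigger is 1.5 × b; at the eligibility ceiling it is 1.5 × 5 = 7.5 × ULN, sustained for at least a week. The Grade 2 row instead uses an absolute restart grade, 0-1. The text does not say whether the footnote also applies to a patient whose drug-related event sits in the Grade 2 row.

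**Size in the safety tables.** No event frequency is given, so the expected number affected cannot be computed. If all 31 planned patients are treated, each one classified differently changes a discontinuation proportion by 1/31 = 3.2 percentage points.

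**The case against.** The best defense is that a Grade 4 event and a life-threatening event are not quite the same thing here. The seriousness section of Table 8 defines life-threatening separately, as immediate risk of death in the investigator's view. On that reading the row handles the grade and the note steps in only when there is such a risk. This narrows the overlap but does not remove it: a Grade 4 hyperglycemia or hypophysitis with immediate risk of death still falls under both instructions.

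A second defense is that a specific row overrides a general note, so the endocrine rows are tacit exceptions. The table does not say so, and Grade 4 hyperthyroidism, also endocrine, is permanently stopped. No general endocrine exemption can be inferred.

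A third is that the trial has other protections. Section 6.2 halts accrual after one Grade 5 or two Grade 4 related events, and Section 8.1 provides monthly review. Section 6.4.1 keeps all treated patients in the response and survival analyses. These points stand and limit the trial-level effect, but none decides whether a given patient is re-dosed.

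A reader might also infer more than the text supports:

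- **All Grade 4 endocrine events conflict with the note.** Hyperthyroidism does not.
- **The rows permit unlimited resumption after recurrent Grade 3 events.** They are silent on recurrence, and the note supplies the limit.
- **The hypophysitis cell contradicts itself outright.** It can be read in sequence: restart at Grade 0-1, then carry on while replacement is arranged. Section 4.3.1, which mentions hormone replacement as steroids are tapered, fits that reading. The cell is ambiguous.
- **The liver rows give opposite instructions.** Table 3 covers drug-related events, so an unchanged baseline value triggers nothing, and a hold under the Grade 2 row is compatible with a footnote trigger that has not been met. Worked enzyme examples would need grade cut-offs that the documents adopt by reference but do not print, including how an abnormal baseline is graded.

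**Conclusion.** The contradiction is real for two rows, type 1 diabetes/hyperglycemia and hypophysitis, at Grade 4. Hypothyroidism joins them at Grade 4 only, as continue against stop. This rests on Table 8's description of Grade 4; under the narrower seriousness definition the conflict shrinks to events with immediate risk of death but remains. The hypophysitis restart cell and the reach of footnote a are secondary ambiguities, not opposite instructions.

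The number of patients affected cannot be estimated from the documents. The documents do not support any claim that the response-rate test or its error rates are altered. The point merits correction because Table 3 directs treatment and the conflict concerns giving the drug again after a life-threatening event.

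**What to change.** The sponsor should:

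1. Reconcile the hyperglycemia, hypophysitis and hypothyroidism rows with the closing note and state which governs when they differ, including whether life-threatening in the note means Grade 4 or the seriousness criterion in Table 8.
2. State how the two sentences in the hypophysitis restart cell relate.
3. State which AST/ALT rows footnote a governs and how it fits with the Grade 2 restart rule.

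Which clinical rule is right is for the sponsor to decide. The cost is amendment wording to one table and its notes, with no added visits or patients.
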